12.5 Study Endpoint Assessment

12.5.1 Primary Endpoint

Composite Morbidity-Mortality Outcome

The composite morbidity-mortality outcome will be met if any of the following occur after surgery but before hospital discharge: death, cardiac arrest, extracorporeal membrane oxygenation, renal insufficiency (creatinine more than two times normal), hepatic insufficiency (aspartate aminotransferase or alanine aminotransferase more than two times normal >36 hours

post-op), or lactic acidosis (>5mmol/L, that is increasing). This outcome is ideal because death rarely occurs in this population. Similar to others^{107,114,115}, we have found this endpoint to be highly associated with other important clinical outcomes in this population (Table 1).¹¹⁷

A secondary analysis will be performed on the incidence of the Composite Morbidity-Mortality Outcome at 30 days post cardiac surgery (regardless of hospital discharge status).

12.5.2 Secondary Endpoints

- CPB data (minutes)
 - duration of Deep Hypothermic Circulatory Arrest (DHCA) (if utilized)
 - total duration of CPB
 - duration of myocardial ischemia (cross clamp time)
- Inotropic Score and Vaso-active Inotropic Score

Inotropic score is calculated by the equation:
(dopamine+dobutamine) + (milrinone x10) + [(epinephrine+norepinephrine+isoproterenol)x100]. All drug doses are in micrograms/kg/min.
- Vasoactive Inotropic score is calculated by the equation:
(dopamine+dobutamine)] + (milrinone x10) + [(epinephrine+norepinephrine+isoproterenol)x100] + (vasopressin x10). All drug doses are in micrograms/kg/min except vasopressin which is miliunits/kg/min. To convert vasopressin from units/kg/min to miliunits/kg/min multiply by 1,000 and inserted into the equation.
- LCOS – Assessed over the first 36 hours

LCOS will be determined to be present if there are clinical signs and symptoms (e.g., tachycardia, oliguria, cold extremities) which required one or more of the following interventions during the initial 36 hours post admission from the operating room: mechanical circulatory support, escalation of existing pharmacological circulatory support to >100% over baseline, or initiation of new pharmacological circulatory support. Despite the inherent subjectivity of this definition, it imposes no additional risk to calculate and will be included as a secondary endpoint.
- Hemodynamic Parameters

Vital Signs: Heart rate, systolic, diastolic and mean arterial pressures and pulse oximeter saturation
Left and right atrial pressures when monitoring lines are present
Cerebral and somatic (renal) near infrared spectroscopy (NIRS) when present
- Laboratory Parameters

Hematology: complete blood count (CBC)
Biochemistry: Na⁺, K⁺, Cl⁻, HCO₃, BUN, creatinine, glucose, AST, ALT, alkaline phosphatase, total protein, albumin and total bilirubin.
Arterial Blood Gas: PO₂, PCO₂, pH, HCO₃, Lactate, Ionized Calcium

These laboratory tests are standard of care and not required by the study. When available they will be recorded at the time points described in Table 2.

- Acute Kidney Injury

The Acute Kidney Injury Network's criteria for acute kidney injury will be applied.¹⁰⁹ Specifically, postoperative acute kidney injury will be defined as an increase in serum creatinine above the pre-operative level by either an absolute value of >0.3 mg/dL, a $\geq 50\%$ increase or urine output below 0.5 mL/kg/hr over a 6 hour period.

- Other Parameters

Duration mechanical ventilation (hours), ICU stay (hours), and hospitalization (days) Fluid intake (ml) and urine output (ml). In addition the number of days alive and out of the hospital at 90 days post cardiac surgery will be recorded.

- Bayley Scales of Infant Development

The Bayley Scales of Infant Development (BSID-III is the current version) is a standard series of measurements used primarily to assess the motor (fine and gross), language (receptive and expressive), and cognitive development of infants and toddlers, ages 0-3. This measure consists of a series of developmental play tasks and takes between 45 - 60 minutes to administer. Raw scores of successfully completed items are converted to scale scores and to composite scores. These scores are used to determine the child's performance compared with norms taken from typically developing children of their age. This will be performed in conjunction with an evaluation from a specialist in Developmental Pediatrics at 12 months of age.

The results of this evaluation will be made available to the parent(s)/LAR and pediatrician. Appropriate consultation with occupational, physical or speech therapist or follow up with Developmental Pediatrics will be made based on the specialist recommendations.

- Hemodynamics and Post-operative Course

During the operative period, hemodynamic values will be recorded at time intervals coinciding with the blood collection. All measurements will be obtained from the catheters and monitors in place for the normal clinical conduct of the surgical procedure. In the postoperative period, the requirement for inotropic medications, duration of intubation and mechanical ventilation, duration of ICU and hospital stay, and fluid status will be documented from existing medical documentation. Any data obtained through the course of the study may be used for clinical management of the patient. Data related to the level of circulating biomarkers will be collected but run in batch at a core laboratory, therefore this will not be immediately available for direct patient care. All historical and demographic data will come from existing records.

- Quantitative Measures of Inflammatory Biomarkers

Whole blood samples of 5 ml will be collected in a heparinized tube at critical peri/post-operative time points for the measurement of markers of oxidative stress, organ damage, cytokines, MMPs, and miRNAs. During the cooling and rewarming phases of CPB, routine clinical measurements of activated clotting time (ACT) are performed. The remaining

discarded plasma will be retained for additional analysis. This approach minimizes blood loss and provides additional CPB time points for analysis. Plasma will be isolated by centrifugation, decanted into aliquots and stored at -80°C until processed for immunoassays. All samples will be batched and run simultaneously to avoid potential laboratory assay variance. The list chosen here is not exhaustive, and would be expected to change as new information is discovered over the course of this study. The time course for the proposed measurements has been designed to minimize blood draws.

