**Corticosteroid Therapy in Neonates Undergoing Cardiopulmonary Bypass
(Steroids in Neonatal Cardiac Surgery)**

Version 7.0 / Date: 09/15/2014 Grant# R01 HL112968

PRINCIPAL INVESTIGATOR

PRINCIPAL INVESTIGATOR

[name]
Associate Professor
MUSC
[name]
[name]
[name]
[contact]
[contact]
E-mail: [contact]

BIostatistician

BIostatistician

[name]
Assistant Professor
MUSC
[name]
[name]
[name]
[contact]
[contact]
E-mail: [contact]

NHLBI PROGRAM OFFICER

[name]

NHLBI
[contact]
[contact]

Protocol Synopsis

Title	Corticosteroid Therapy in Neonates Undergoing Cardiopulmonary Bypass
Short Title	Steroids in Neonatal Cardiac Surgery
Clinical Phase	Phase IV
IND Number	Exempt
Rational for Study Population	The study will focus on neonates for a few reasons. Although their post- cardiopulmonary bypass (CPB) clinical course is typically more severe and ICU care more prolonged than older children, their modes of morbidity are also well characterized. Further, the high level of severity itself provides a substrate for identifying the positive effects of a particular therapy. Finally, a therapy identified as beneficial has the greatest potential for benefit in this vulnerable population.
Primary Aim	Compare the effects of intraoperative methylprednisolone (MP) to placebo on morbidity and mortality following neonatal cardiopulmonary bypass (CPB).
Hypothesis	Neonates receiving MP will have an improved perioperative clinical course as assessed by a decrease in morbidity and mortality and evidence of capillary leak.
Study Design	Multi-center, prospective, randomized, double blind, placebo-controlled study of intraoperative MP in neonates undergoing cardiac bypass (CPB). Randomization into one of the 2 study groups in the ratio of 1:1. The randomization will be stratified by corrective vs. palliative surgery and by surgeon.
Primary Endpoint	Incidence of a clinically derived composite morbidity-mortality outcome
Secondary Endpoint	
 - Inotropic score over the first 36 hours after surgery - Incidence of low cardiac output syndrome over 36 hours - Urine output over 36 hours - Total intake/output of fluid over 36 hours - Duration of mechanical ventilation, ICU and hospital length of stay - Days alive & out of hospital at 90 days - Bayley Scale of Infant Development at 1 year - Inflammatory markers

	- Adverse Events

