1.2 Hypothesis/Research Question

Neonates receiving MP will have an improved perioperative clinical course as assessed by a decrease in morbidity and mortality and evidence of capillary leak.

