7.1.5 Postoperative Management

All patients will be managed postoperatively in a dedicated pediatric cardiac intensive care unit by both a cardiac intensivist and cardiothoracic surgeon. Hemodynamic monitoring will minimally consist of ECG, invasive beat to beat arterial blood pressure, pulse oximetry, and noninvasive blood pressure. A urinary catheter will be used to assess total urinary output during the first 36 hours. hematology, biochemistry, blood gases, lactate and ionized calcium may be performed at the discretion of the attending physician. Cardiovascular medication will not be standardized, but will be recorded in the CRFs. To allow for the calculation of a vaso-active inotropic score^{37, 107}, the doses of inotropic medications will be recorded at admission to the ICU from the operating room and every 4-12 hours for 36 hours. The highest hourly inotropic score and vaso-active inotropic score over the first 36 hours postoperatively will also be recorded. Routine use of postoperative steroids will be discouraged.

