12.3 Subgroup Analyses

The modified ITT population, defined as the set of all patients randomized to treatment and underwent cardiopulmonary bypass, will be analyzed and presented for the Primary Endpoint. The same analyses will be conducted on the PP population, defined as those patients who are randomized, receive study drug as defined in the protocol, and have no major protocol violations preventing analysis (e.g. – post-op patients who receive steroids off-protocol). A two-sided test

with alpha of 0.05 will be used. The following subgroups will be analyzed for the Primary Endpoint:

Underlying diagnosis:	Palliated vs. Corrective procedure
Age:	≤ 7 days vs. >7 days
Body weight:	≤ 2.5 kg vs. >2.5 kg

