12.6 Study Data Collection

12.6.1 Table 2: Schedule of Measurements

	(a)PREOP	(c)T=1, 2 OR	PCICU	T=3 4 hrs ± 1 hr	8 hrs ± 1 hr	T=4 12 hr ± 1 hr	T=5 24 hr ± 1 hr	36 hr ± 1 hr	D/C	30 days Post- op	90 days Post- op	1 Year Followup 12-14 Months
Windows			Arrival									
Informed Consent	X											
Inclusion/Exclusion	X											
Demographics	X											
Diagnosis Details		X										
Med/Surg History	X							X				
Randomization	X											
Vital Signs	X		X	X	X	X	X	X				
ABG, Ion Ca ⁺⁺ , Lactate (e)	X		X	X	X	X	X	X				
Hematology (e)	X		X				X	X				
Biochemistry (e)	X		X				X	X				
Diuretics								X				
Biomarker		(b)XX		X		X	X					
Urine Sample		X	X				X					
Cardio-Pulmonary Bypass (CPB)		X										
Daily Inotropic Scores	X		X	X	X	X	X	X				
Highest Inotropic Score								X				
36 HR Assessment								X				
I/O (d)						X		X				
LCOS								X				
Duration of Ventilation									X			
Length of ICU & Hospital Stay									X			
Composite Outcome									X	X		
Days alive & out of hospital											X	
Bayley Scale												X
Study Completion												X
Adverse Events	X	X	X	X	X	X	X	X	X			X

- (a) Last Values before Surgery
- (b) 2 Biomarker Samples in OR regardless of time
- (c) T= Time point of blood/urine sample for study
- (d) I/O collected 1 day post-op
- (e) These laboratory values are standard of care and will be recorded at these time points if obtained. They are not required

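### The 36-hour fluid intake and urine output endpoints are given only in absolute millilitres, so weight differences between infants add avoidable noise to them

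*Combined protocol and SAP*

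**What the plan says.** The Protocol Synopsis lists "Urine output over 36 hours" and "Total intake/output of fluid over 36 hours" among the secondary endpoints, and section 4.1.2 lists fluid balance over the first 36 hours. The only statement of the variables is in section 12.5.2, under Other Parameters: "Fluid intake (ml) and urine output (ml", in a list that also gives ventilation and ICU stay in hours and hospitalization in days.

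Elsewhere the plan does scale for size. In the same section the acute kidney injury criterion uses "urine output below 0.5 mL/kg/hr over a 6 hour period", and both inotropic scores are built from doses per kilogram per minute. Section 8 sets the study drug volume by body weight. Section 12.3 plans a primary-endpoint subgroup at "≤ 2.5 kg vs. >2.5 kg".

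For continuous variables, sections 12.4 and 12.10 plan ANCOVA with the baseline value of the variable as covariate. Adjustment for diagnosis and surgeon is stated for the primary analysis.

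On timing, section 7.1.5 says "A urinary catheter will be used to assess total urinary output during the first 36 hours". In Table 2 the intake/output row appears to carry marks at 12 and 36 hours, while footnote (d) reads "I/O collected 1 day post-op".

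**The concern.** A larger neonate is given more fluid and passes more urine for reasons unrelated to methylprednisolone. If the analysed variable is a raw total, that variation sits in the error term, and nothing in the plan takes it out:

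- A postoperative 36-hour volume has no natural baseline value, so the planned ANCOVA covariate does not help.
- Randomization is stratified by operation and surgeon, not weight.
- Correcting significant baseline imbalances deals with chance differences between arms, not with the spread of weights within each arm.

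The hypothesis in section 1.2 is to be judged "as assessed by a decrease in morbidity and mortality and evidence of capillary leak". No endpoint is labelled as the measure of capillary leak. Fluid balance is the closest clinical one, but that is an inference. At stake is the chance of detecting a real effect on intake or urine output with 95 infants per arm.

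**Working it through.** **1. The plan's only fluid figure.** Section 1.3.1 reports a diuresis difference of -96 ± 49 mL, p = 0.05, in arms of 39 and 37. Read as a standard error, 96/49 = 1.96, so p = 0.050 (normal) or 0.054 (t, 74 df). Read as a per-patient SD, t would be about 8.5, which is incompatible with p = 0.05. So 49 is a standard error, and the implied between-infant SD is 49/√(1/39 + 1/37) = 49/0.2295 ≈ 213.5 mL.

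At that SD with 95 per arm, the standard error is 213.5 × √(2/95) ≈ 31.0 mL. Power for 96 mL is Φ(96/31.0 − 1.96) ≈ 87%, and the difference detectable with 80% power is 2.80 × 31.0 ≈ 87 mL. The documents state no power for a fluid endpoint.

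**2. Noise from weight in a positive total.** The documents give no SD of weight, no mean volume and no CV of volume, so all three inputs here are assumptions: weight CV w = 12-20% (middle value 16%), per-kilogram volume CV c = 30-50%, and volume = weight × volume per kilogram, with the two factors independent. Then

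ratio = (c² + w² + c²w²)/c² = 1 + w²/c² + w².

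The equivalent number of infants is 190/ratio. Power in mL, for an effect that has 80% power per kilogram, is Φ(2.80/√ratio − 1.96).

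| w | c | Variance ratio | Equivalent n of 190 | Power in mL |
|---|---|---|---|---|
| 12% | 50% | 1 + 0.0576 + 0.0144 = 1.07 | 177 | 77% |
| 16% | 50% | 1 + 0.1024 + 0.0256 = 1.13 | 168 | 75% |
| 16% | 40% | 1 + 0.1600 + 0.0256 = 1.19 | 160 | 73% |
| 16% | 30% | 1 + 0.2844 + 0.0256 = 1.31 | 145 | 69% |
| 20% | 30% | 1 + 0.4444 + 0.0400 = 1.48 | 128 | 63% |

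**3. Tied to the prior-trial SD.** If the SD is 213.5 mL, the mean volume is 200-600 mL and w is 10-20% (the last two assumed), removing weight variation raises the 87% power for 96 mL to between 88% and 97%.

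**4. Net balance.** For a difference with mean m, weight contributes about (w·m)² to the variance. With m = 150 mL and w = 20%, (0.20 × 150)²/213.5² = 900/45,582 ≈ 2%. For a mean nearer zero it is less.

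**5. If output is not proportional to weight.** Let volume vary as weight to the power b. To first order, the weight term in the squared CV is b²w² for the mL total and (1 − b)²w² for the mL/kg ratio. The ratio is the less noisy of the two when b exceeds 0.5. It over-corrects somewhat when b is below 1. A weight covariate estimates the slope instead of fixing it.

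**6. Observation time.** A uniform ± 1 hour window around 36 hours has CV (1/√3)/36 = 1.6% and costs 0.1 percentage point of power or less.

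**The case against.** The strongest objection is that section 12.5.2 lists units of recording, not analysis variables, and that section 12.11 refers to a subsequent SAP where the scale could be set. That is a fair reading of one line. But the line is the only definition these endpoints have, it sits in the endpoint assessment section, and no other text indexes them or adjusts for weight. The SAP is a suitable place for the repair.

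A second objection is that mL matches the prior trial, whose SD already implies 87% power for the difference seen there. This stands as a reason to keep reporting mL totals. It does not make mL the more precise scale, since that SD already includes weight variation.

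A third is that the size of the loss is entirely assumed. This stands. The 2.5 kg cut-point shows a planned subgroup, not how widely weights vary. Under the product model, the three 16% rows imply mean totals of roughly 400 to 620 mL at an SD of 213.5 mL, and the documents state no mean.

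A reader might also infer that totals in mL are distorted by unequal hours of observation, for instance after an early death, and that dividing by hours observed would repair this. The documents do not support that. The visit window costs almost nothing, section 12.5.1 says death is rare in this population, and no frequency of short records is given. An hourly rate from an infant who dies early is still not comparable with a 36-hour average: section 1.1.3 places the fall in cardiac index typically at 6 to 18 hours after surgery, so the rate covers a different phase of recovery.

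**Conclusion.** The point holds as a minor loss of precision on fluid intake and urine output. The relative variance of a total in mL is about 1.07 to 1.48 times that of the mL/kg value, given a weight CV of 12-20%, a per-kilogram CV of 30-50%, proportional scaling and independence. None of these inputs comes from the documents.

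Two stronger readings should be resisted. One is that the treatment comparison is biased: under 1:1 randomization, weight variation adds noise and does not systematically favour an arm. The other is that the plan's test of capillary leak loses the equivalent of dozens of infants. The equivalent-n figures apply to positive totals only. For a net balance averaging 150 mL or less, weight adds about 2% of variance or less (weight CV up to 20%, SD 213.5 mL), so indexing gains almost nothing there.

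The primary endpoint and the sample size of 190 are unaffected.

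**What to change.** In section 12.5.2, or in the SAP, define the analysed variables as fluid intake, urine output and net balance in mL/kg over the 36-hour window, using the weight already recorded for dosing. Alternatively, keep mL and add body weight as a covariate. Choose one before unblinding, and report mL totals descriptively for comparison with the prior trial.

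Reconcile the 36-hour window in the Synopsis and sections 4.1.2 and 7.1.5 with footnote (d) of Table 2, which could describe either the period covered or the day of recording. State separately how an infant with less than the full period of record is handled, and do not rely on division by hours observed for early deaths.

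The cost is wording only, since weight is already needed for dosing and the weight subgroup. The one small downside is that mL/kg over-corrects somewhat if output rises less than in proportion to weight. The covariate version avoids this.

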12.6 Study Data Collection

12.6.1 Table 2: Schedule of Measurements

	(a)PREOP	(c)T=1, 2 OR	PCICU	T=3 4 hrs ± 1 hr	8 hrs ± 1 hr	T=4 12 hr ± 1 hr	T=5 24 hr ± 1 hr	36 hr ± 1 hr	D/C	30 days Post- op	90 days Post- op	1 Year Followup 12-14 Months
Windows			Arrival									
Informed Consent	X											
Inclusion/Exclusion	X											
Demographics	X											
Diagnosis Details		X										
Med/Surg History	X							X				
Randomization	X											
Vital Signs	X		X	X	X	X	X	X				
ABG, Ion Ca ⁺⁺ , Lactate (e)	X		X	X	X	X	X	X				
Hematology (e)	X		X				X	X				
Biochemistry (e)	X		X				X	X				
Diuretics								X				
Biomarker		(b)XX		X		X	X					
Urine Sample		X	X				X					
Cardio-Pulmonary Bypass (CPB)		X										
Daily Inotropic Scores	X		X	X	X	X	X	X				
Highest Inotropic Score								X				
36 HR Assessment								X				
I/O (d)						X		X				
LCOS								X				
Duration of Ventilation									X			
Length of ICU & Hospital Stay									X			
Composite Outcome									X	X		
Days alive & out of hospital											X	
Bayley Scale												X
Study Completion												X
Adverse Events	X	X	X	X	X	X	X	X	X			X

- (a) Last Values before Surgery
- (b) 2 Biomarker Samples in OR regardless of time
- (c) T= Time point of blood/urine sample for study
- (d) I/O collected 1 day post-op
- (e) These laboratory values are standard of care and will be recorded at these time points if obtained. They are not required

12.6.2 Medical and Surgical History

Medical history will be collected, including the existence of current signs and symptoms and clinical significance for each body system.

12.6.3 Study Completion

The percent of participants who complete the study, losses to follow-up, times to lost to follow-up, and reasons for discontinuation (e.g., adverse events) will be presented. Sample Size and Power Calculations

Some missing data are inevitable in any clinical study. The study will make every effort to minimize missing data through rigorous study procedures. However, when missing data occur, we will take steps in the analysis plan to understand any potential biases stemming from the missing data and to both describe and account for them. These methods include a comparison of those with and without missing data, documentation of sources of missing data, and evaluations of the pattern of missingness.

12.7 Sample Size and Power Calculation For Primary Endpoint

Using data from the previous steroid study performed by [name] the incidence of a similar composite endpoint occurred in 33% of the subjects. This proposed study is powered to detect an absolute difference of 20% between groups. Enrollment of 190 patients (95 per treatment group) will be required to provide 80% power to detect this difference between groups, with an experiment-wise alpha of 0.05 (two-sided), allowing for 1 interim look at the data to assess for superiority and futility. The power analysis was performed using Cytel's East software package (Cambridge, MA) and assumes an O'Brien Fleming alpha spending function.

12.8 Sample Size and Power Calculation for Secondary Endpoints

From the wide variety of Secondary Endpoints, a subset have available data to statistically assess whether or not they are adequately powered from the enrollment necessary to power the Primary Endpoint.

- ICU Length of Stay (LOS). Preliminary data suggest that ICU LOS data are highly skewed in this population, with 20% having ICU LOS > 10 days. We performed statistical simulations (with 5,000 replications) in which we assumed that 40% of subjects receiving placebo would have ICU LOS > 10 days but similar distribution within the ≤10 day and >10 day categories, and under such assumptions we found that having 95 subjects per group provided about 75% power to detect a difference of this magnitude.
- Maximum Inotropic Score Over 36 Hours. Graham⁵ found maximum inotropic scores over the first 36 hours postoperatively of 14.4 ± 3.6 vs. 15.0 ± 3.9 for intraoperative MP alone vs. combined preoperative and operative MP. Assuming similar standard deviations in this study, 95 patients per arm with analyzable data will provide >95% power to detect a difference of ≥ 2 between groups.
- Neurodevelopmental Outcomes. The Pediatric Heart Network Single Ventricle Reconstruction Trial⁴⁷, evaluated neurodevelopmental outcomes at 12 months of age using

the Bayley Scales of Infant Development. Their results revealed a mental scale raw score of 91.93 with a standard deviation of 7.25 in 172 infants undergoing staged palliation for hypoplastic left heart syndrome and related variants. Although dropout is unlikely prior to assessing the primary endpoint, it is more likely prior to the 12 month follow-up. Assuming a similar standard deviation and a 15% dropout rate, 81 patients per arm with analyzable data will provide 99% power to detect a difference of 5 points.

